Appendix 5. PCL-5 PTSD checklist

| No. | Response | Not at all (0) | A little bit (1) | Moderately (2) | Quite a bit (3) | Extremely (4) |
|-----|---|-------------------|---------------------|-------------------|--------------------|------------------|
| 1 | Repeated, disturbing, and unwanted memories of the stressful experience? | 0 | 1 | 2 | 3 | 4 |
| 2 | Repeated, disturbing dreams of the stressful experience? | 0 | 1 | 2 | 3 | 4 |
| 3 | Suddenly feeling or acting as if the stressful experience were actually happening again (as if you were actually back there reliving it)? | 0 | 1 | 2 | 3 | 4 |
| 4 | Feeling very upset when something reminded you of the stressful experience? | 0 | 1 | 2 | 3 | 4 |
| 5 | Having strong physical reactions when something reminded you of the stressful experience (for example, heart pounding, trouble breathing, sweating)? | 0 | 1 | 2 | 3 | 4 |
| 6 | Avoiding memories, thoughts, or feelings related to the stressful experience? | 0 | 1 | 2 | 3 | 4 |
| 7 | Avoiding external reminders of the stressful experience (for example, people, places, conversations, activities, objects, or situations)? | 0 | 1 | 2 | 3 | 4 |
| 8 | Trouble remembering important parts of the stressful experience? | 0 | 1 | 2 | 3 | 4 |
| 9 | Having strong negative beliefs about yourself, other people, or the world (for example, having thoughts such as: I am bad, there is something seriously wrong with me, no one can be trusted, the world is completely dangerous)? | 0 | 1 | 2 | 3 | 4 |
| 10 | Blaming yourself or someone else for the stressful experience or what happened after it? | 0 | 1 | 2 | 3 | 4 |

| | | | | | | |
|----|---|---|---|---|---|---|
| 11 | Having strong negative feelings such as fear, horror, anger, guilt, or shame? | 0 | 1 | 2 | 3 | 4 |
| 12 | Loss of interest in activities that you used to enjoy? | 0 | 1 | 2 | 3 | 4 |
| 13 | Feeling distant or cut off from other people? | 0 | 1 | 2 | 3 | 4 |
| 14 | Trouble experiencing positive feelings (for example, being unable to feel happiness or have loving feelings for people close to you)? | 0 | 1 | 2 | 3 | 4 |
| 15 | Irritable behavior, angry outbursts, or acting aggressively? | 0 | 1 | 2 | 3 | 4 |
| 16 | Taking too many risks or doing things that could cause you harm? | 0 | 1 | 2 | 3 | 4 |
| 17 | Being "superalert" or watchful or on guard? | 0 | 1 | 2 | 3 | 4 |
| 18 | Feeling jumpy or easily startled? | 0 | 1 | 2 | 3 | 4 |
| 19 | Having difficulty concentrating? | 0 | 1 | 2 | 3 | 4 |
| 20 | Trouble falling or staying asleep? | 0 | 1 | 2 | 3 | 4 |

Adapted from Weathers FW, Litz BT, Keane TM, Palmier PA, Marx BP, Schnurr, PP. (2013). The PTSD Checklist for DSM-5 (PCL-5) – Standard [Measurement instrument]. Available from <http://www.ptsd.va.gov/professional/assessment/adult-sr/ptsd-checklist.asp>

Appendix 6. Post-natal PTSD risk factors questions

1. Infant complications

A. Gestational age

≥ 37/40 <37/40 (pre-term)
 Don't know

B. Perinatal outcome

Live birth Still birth
 Early neonatal death (<7/7)

C. Birth weight

≥ 2500g (≥ 5lb 8oz) 1500-2499g
 <1500g (<3lb 5oz) Don't know

D. Admission to neonatal ICU

No: Yes:

2. Maternal mental wellbeing

A. Psychological disorder prior to or during index pregnancy

None: Depression:
 Anxiety trait or panic attacks: Previous PTSD:

B. Postpartum depression

No: Yes:

3. Maternal support

A. Please rate the quality of support you have received from healthcare professionals (e.g., hospital staff, midwife, GP). Please rate on a scale of 0 (no support) to 4 (excellent support).

| | | | | |
|-------------------|-------------------------|-------------------------|-------------------------------|--------------------------|
| No support (0) | A little support (1) | Moderate support (2) | Quite a bit of support (3) | Excellent support (4) |
|-------------------|-------------------------|-------------------------|-------------------------------|--------------------------|

B. How much do friends and family support you?

| | | | | |
|-------------------|-------------------------|-------------------------|-------------------------------|--------------------------|
| No support (0) | A little support (1) | Moderate support (2) | Quite a bit of support (3) | Excellent support (4) |
|-------------------|-------------------------|-------------------------|-------------------------------|--------------------------|

Appendix 7. AAGA Extended follow up questions

Part 1. Have you had any further memories, recollections or thoughts about your experience during the anaesthetic?

Part 2. Please think back to the time when your first remembered having an awareness experience.

Did you want to speak to a member of the anaesthetic team at your local hospital about your awareness experience?

Yes No

Was the opportunity made available for you to speak a member of the anaesthetic team at your local hospital?

Face to face meeting:

Yes No

Telephone discussion:

Yes No

Other _____

If you had a meeting, then when did this take place?

Within 24 hours of reporting having awareness

1-2 days after reporting awareness

3-7 days after reporting awareness

>7 days after reporting awareness

Before hospital discharge After hospital discharge

Did you feel that the local team listened to your story and experience?

Yes No

Did anyone apologise or express regret to you about your experience?

Yes No

Who else have you seen as part of your follow up for your awareness experience?

Please rank how helpful you found each specialist, relative to others (please rank as 1 the specialist that offered you the most emotional or practical support to enable you to understand and come to terms with your experience).

Anaesthetist How many meetings? _____ Rank _____

Clinical Psychologist How many meetings? _____ Rank _____

Psychiatrist How many meetings? _____ Rank _____

GP How many meetings? _____ Rank _____

Counsellor How many meetings? _____ Rank _____

Other _____ How many meetings? _____ Rank _____

If you haven't already then would you like to speak to any of the following:

Clinical Psychologist Psychiatrist
 GP Counsellor

Did you receive any feedback regarding any local investigation that may have taken place to find the cause of your awareness incident?

Yes No

How would you grade the quality of support you received following reporting your awareness event?

| | | | | |
|------------------|-------------|-----------------|-------------|------------------|
| Very poor (0) | Poor (1) | Moderate (2) | Good (3) | Very good (4) |
|------------------|-------------|-----------------|-------------|------------------|

What aspects of your post-awareness support did you find particularly helpful?

What aspects of your post-awareness support did you not find helpful?

How might you improve post-awareness support for other patients?

Part 3. How do you feel now about having an anaesthetic again?

Have you received another general anaesthetic since your experience?

Yes No

If so, then how many?

What was your experience around the subsequent general anaesthetics?

Part 4. Do you feel that your awareness experience has impacted upon your ability to care for your baby? If so, then how?

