The default follow up methodology for encounters led by the DREAMY Research Team will be telephone structured interview schedules. At the start of the study equivalent written/email questionnaire forms of the interview questions will be provided to maximise follow up data collection. Alignment of responses between different data collection formats will be maximised by using interview schedules structured identically to paper questionnaires and presenting both with simple, equivalent contextual information. During interim analysis if a response format (i.e. telephone, face-to-face or written) is found to be infrequently selected by participants, then this choice may later be removed to further maximise data concordance.

"Brice positive" respondents will receive targeted questions on risk factors for post-natal PTSD ([Appendix 6](#)) during 30 day follow up and be offered the PCL-5 PTSD checklist ([Appendix 5](#)) at 30 days, 3, 6, 9 and 12 months following the index anaesthetic episode. The questions and checklist will be administered by telephone (or via email, at participant request) by the DREAMY Research Team.

An extended questionnaire for "Brice positive" participants will also be undertaken during the 3 month PTSD follow up episode ([Appendix 7](#)). This questionnaire is designed to explore the nature of local clinical follow received by patients and how the AAGA episode has impacted on attitudes towards future anaesthetics and post-natal experience.

Anaesthetic episode data collection will be conducted retrospectively by the anaesthetic Local Investigators from patient notes and anaesthetic records after each participant has provided written consent for study involvement. Data collected on the anaesthetic episode is detailed in [Appendix 3](#) and includes: age of patient, parity, procedure, urgency of surgery/LSCS, ASA status, booking BMI, anaesthesia start/finish time, induction agents (and doses), de novo or conversion to GA, indication for GA, rapid sequence induction, maintenance agent, nitrous oxide use, MAC, (lowest, highest, estimated median), primary airway device, difficult intubation, grade of laryngoscopy, local/regional anaesthesia, neuromuscular blockade, nerve stimulator use, reversal use, depth of anaesthesia monitor use, most senior anaesthetist present, location of extubation, post op destination, estimated blood loss.

1. 0h = Time of GA for obstetric indication surgery.

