2. 0-24h following index GA = Written consent obtained. Modified Brice questionnaire (repetition 1). Data collected for the anaesthetic episode.
3. 24-48h following index GA = Modified Brice questionnaire (repetition 2).
4. Day 30 (+/- 5 days) from index GA = Modified Brice questionnaire (repetition 3).

If a participant reports possible recall of events during the anaesthetic episode (“Brice positive”):

1. Participants will be offered a further Suspected AAGA structured interview schedule or questionnaire (adapted from the BAG-RECALL trial [Avidan 2011]). Questionnaires are available in paper form for distribution to inpatients by Local Investigators. Interviews can be conducted via telephone or face-to-face. Suspected AAGA follow up will be made at the earliest available opportunity and in a format of the participant’s preference.
2. “Brice positive” notification will be shared between the local clinical teams and the DREAMY Research Team.
3. Local clinical care teams will be encouraged to offer care in accordance with the NAP5 awareness support pathway [NAP5 Anaesthesia Awareness Support Pathway].
4. Post-Traumatic Stress Disorder (PTSD) Checklist (PCL-5) at day 30, 3, 6, 9 and 12 months.
5. Post-natal PTSD risk factor questions at day 30.
6. AAGA Extended follow up at 3 months, exploring patient attitudes and post-AAGA clinical support.

An initial minimum sample of the first 300 Brice -ve patients completing day 30 follow up will also receive:

1. PCL-5 checklist and targeted questions on risk factors for post-natal PTSD at day 30. This provides a comparator group for PTSD incidence and baseline characteristics in the post-natal period for AAGA vs. non-AAGA patients.

Figure 2. Summary of in-hospital, telephone and conditional DREAMY data collection procedures

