All suspected AAGA patients will also be offered the PCL-5 PTSD checklist ([Appendix 5](#)) at day 30, 3, 6, 9 and 12 months following the index anaesthetic episode. The checklist will be administered via telephone by the DREAMY Research Team (although written forms or face-to-face will be provided if requested). During first administration of the PCL-5 checklist additional target information will be obtained using a structured and multi-dimensional questionnaire on the woman's self-reported mental health history, infant's health status and psychological experiences in the gravidic-puerperal cycle. Question domains have been derived from known risk factors for developing PTSD during the post-natal period [Andersen 2012] and will also be asked to the comparator sample of 300 non-AAGA patients collected during the early phase of the study (see [Section 6.5](#)).

An extended AAGA follow up will occur during the 3 month PTSD follow up episode, with a view to investigating the nature of local clinical follow up received by patients and how the AAGA episode has impacted on attitudes towards future anaesthetics and post-natal experience (see [Appendix 7](#) for questions used).

[figure not shown]

Figure 4. Suspected AAGA Follow Up flowchart

10 Data management and quality assurance

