Before any site can enrol patients into the study, the Principal Investigator must be granted written NHS R&D approval – confirmation of capacity and capability.

The site must conduct the study in compliance with the protocol, as agreed by the Sponsor and as given favourable opinion by the Research Ethics Committee (REC) and HRA.

The Chief Investigator will be provided (via the Sponsor) with file indices E.G. JREODOC0003 TMF index and JREODOC0004 ISF index for use with SOP JREOSOP0019 'Preparation and Maintenance of the TMF' The CI will be responsible for the maintenance of the TMF and may delegate the responsibility of ISF file maintenance to the PI at each participating site.

It is the responsibility of the Principal Investigator at each site to ensure that all subsequent amendments gain the necessary R&D approval. Refer to JREOSOP0011 'Management of Amendments'.

Within 90 days after the end of the study, the CI and Sponsor will ensure that the REC is notified that the study has finished. If the study is terminated prematurely, those reports will be made within 15 days after the end of the study. Refer to JREOSOP0015 'End of study declaration'.

The CI will supply an End of Study report of the clinical study to the REC within one year after the end of the study. The sponsor can provide JREODOC0059 End of Study report template.

The primary ethical issue in any obstetric study is to ensure the welfare of the mother and the baby take priority over any research aims. The psychosocial and physical vulnerability of mothers should always be considered. This study does not involve any physical intervention that could cause any harm or stress. The Brice questionnaire is short and has been designed with the intention that it does not present any significant risk or burden to the patient. However, the patient is under no obligation to participate and complete the questionnaires if they do not wish to.

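### The 3-month question on caring for the baby is printed with no way past it for a bereaved mother, and Appendix 6 has no code for a baby who died at day 7 or later

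*Protocol*

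**What the plan says.** Section 6.2 schedules the Appendix 7 questionnaire for Brice-positive women: it says that an extended questionnaire for these "participants will also be undertaken during the 3 month PTSD follow up episode". The schedule in section 10.2 places it at 3 months, by telephone or as a written questionnaire, and section 6.2 has the interview and paper versions built to the same structure. Part 4 of Appendix 7 is a single open question, "Do you feel that your awareness experience has impacted upon your ability to care for your baby", followed by a prompt to say how if so. The only condition in it concerns impact, not whether the baby is living.

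Appendix 6 item 1B records perinatal outcome in three options: live birth, stillbirth, and "Early neonatal death (<7/7" days). Section 6.2 sets the timing as "Post-natal PTSD risk factor questions at day 30", with a window of 5 days either side in section 10.2. Section 9.3 ties the items to the first PCL-5, when "additional target information will be obtained using a structured and multi-dimensional questionnaire"; no later update is described. The same items go to at least 300 Brice-negative women, and section 6.2 gives their purpose: "This provides a comparator group for PTSD incidence and baseline characteristics in the post-natal period for AAGA vs. non-AAGA patients".

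Sections 7.1 and 7.2 admit women from 24 weeks' gestation and do not exclude those who have lost a baby. Section 14 states: "The psychosocial and physical vulnerability of mothers should always be considered".

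**The concern.** The study recruits women having general anaesthesia for obstetric surgery, including the most urgent caesarean category (Appendix 3), and its own form anticipates perinatal death. Followed as printed, the instruments would ask a bereaved woman, already under PTSD follow-up, how awareness has affected her care of a baby who has died. On paper no interviewer is present to pass over the item.

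The natural filter is item 1B, but it is incomplete. A mother whose baby died in the third week of life has no option that describes her loss. The record would then not warn whoever prepares her 3-month contact, and the loss would be missing from a questionnaire whose domains section 9.3 says come from known risk factors for post-natal PTSD.

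At stake are the welfare of a small number of women and the accuracy of one descriptive item, in Brice-positive women and comparators alike.

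**Working it through.** The protocol states no figure on this point that could be reproduced, so the first check sets the forms against each other. The second gives a scale under stated assumptions.

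**1. What each type of loss meets in the forms**

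| Time of loss | Code in item 1B (day 30 ± 5) | Part 4 at 3 months |
|---|---|---|
| Stillbirth | Own code | Asked; no skip printed |
| Death before day 7 | Own code | Asked; no skip printed |
| Death from day 7 to the call (day 25 to 35) | None: live birth or blank | Asked; record gives no warning |
| Death between the call and 3 months | Not covered; item asked once | Asked; record gives no warning |

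The coding gap is the third row only. The missing skip concerns all four.

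**2. Number of Brice-positive women**

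Section 12.2.2 gives three scenarios for a sample of about 2,250 (section 12.2.1):
- 2,250 / 660 = 3.4, which the plan gives as about 4
- 2,250 / 152 = 14.8, given as about 15
- 2,250 / 19 = 118.4, given as 118

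**3. Chance that at least one of them is bereaved by 3 months**

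The documents give no infant-loss rate. I assume q = 1%, 3% or 5%, purely as a range, and use the plan's rounded case numbers m. The expected number is m × q, and P(at least one) = 1 − (1 − q)^m.

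| m | q = 1% | q = 3% | q = 5% | Expected number, 1% to 5% |
|---|---|---|---|---|
| 4 | 1 − 0.99^4 = 4% | 1 − 0.97^4 = 11% | 1 − 0.95^4 = 19% | 0.04 to 0.20 |
| 15 | 1 − 0.99^15 = 14% | 1 − 0.97^15 = 37% | 1 − 0.95^15 = 54% | 0.15 to 0.75 |
| 118 | 1 − 0.99^118 = 70% | 1 − 0.97^118 = 97% | 1 − 0.95^118 = 99.8% | 1.2 to 5.9 |

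These figures pool all losses by 3 months. They bear on the missing skip and do not measure the coding gap.

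**4. Scale of the coding gap among comparators**

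If 0.05% to 1% of women lose a baby between day 7 and the day-30 call (again an assumption), the 300 comparators would include 300 × 0.0005 = 0.15 to 300 × 0.01 = 3 such women.

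**5. Is anything estimated from these items?**

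Part 4 is free text. The secondary endpoints (section 12.1.2) do not include it, and section 12.2.3 plans no count from it. The only multivariable model in section 12.2.3 relates anaesthetic episode variables to AAGA. Infant outcome is not named as a factor in any PTSD analysis.

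**The case against.** The strongest reply is that this is a matter of form wording with no statistical consequence, and that practice may already cover it. Case report forms are designed separately (section 10.2) and captured in REDCap, and the follow-up flowchart (Figure 4) is not available to read. The appendices do not always print branching: Appendix 2 asks whether dreams were disturbing without a printed skip for women who had none. Telephone is the default, one central team makes both the day-30 and 3-month contacts, and section 14 lets a woman leave questions unanswered. An operational skip therefore cannot be ruled out.

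Much of that stands, but none of the available text provides a skip, and the same instruments do print filters elsewhere. Appendix 4 Part 3 has a not-applicable box, and Appendix 7 Part 2 makes the timing of a meeting conditional on there having been one. A caller's memory or tact is no safeguard on paper.

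A reader might infer more than the documents support:
- **That bereaved mothers in general are miscounted.** Stillbirths and deaths before day 7 have their own codes. For a later death, live birth is literally true as a birth outcome; what it misses is the loss.
- **That the proportion reporting an effect on caring has the wrong denominator.** No such proportion is planned.
- **That late deaths contaminate the reference group of a PTSD risk-factor analysis.** No analysis by infant outcome is specified.
- **That section 14 is contradicted.** It states a general principle, which this item serves poorly; no two rules conflict.

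**Conclusion.** The point holds as a low-cost improvement to two forms. As printed, Part 4 would be put to any bereaved Brice-positive woman reached at 3 months, and item 1B cannot record a death from day 7 up to the day-30 call. No endpoint, test or planned estimate changes.

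Few women are likely to be affected. Under the general-population and earlier obstetric-study scenarios, fewer than one bereaved Brice-positive woman is expected even at a 5% loss rate; under the 118-case scenario about 1 to 6 are expected. All these figures rest on assumed loss rates, and on losses being as common in Brice-positive women as the assumed rate implies. The case for acting rests on a foreseeable and avoidable distress, not on frequency.

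**What to change.** - **Appendix 6, item 1B:** add the option *Baby died at 7 days or later*, for Brice-positive women and comparators alike.
- **Appendix 7, Part 4:** do not ask it when item 1B records a stillbirth or infant death.
- **Appendix 7, Part 4, interview and written versions:** add a lead-in or a not-applicable option, so that a woman whose baby died after the day-30 call, or whose item 1B was blank, can pass over it.

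The third change makes a separate check of infant status before the 3-month contact unnecessary, so no new procedure or data source is needed. The cost is a minor amendment to two forms and one REDCap branch, with no extra visits or staff.
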